#### 6.2.7 Study Closeout

At completion of the study it will be determined whether the access that was randomized into the study is still functional or not. If total site failure has occurred the date of that occurrence will be determined. Hospitalization and mortality data will be obtained using national databases while the study is on-going and for up to five years after the study has ended.

# 7. PRIMARY OUTCOME MEASURE

The primary outcome will be primary unassisted patency defined as the time from randomization until the first occurrence of either of the following:

- 1. Thrombosis
- 2. An access procedure performed or recommended to restore patency including angioplasty, thrombolysis, thrombectomy, or any surgical modification of the graft.

It is stipulated that access surgery done to modify the access because of a steal syndrome or congestive heart failure occurring within the first 30 days after creation of the access will not be considered an event for the primary composite outcome. However, loss of access function for any

reason will be considered a primary outcome. The primary endpoint will also be considered to occur if the subject is found to have a  $\geq$ 50% access stenosis by angiography for which an intervention is recommended but refused.

For patients who are undergoing regular hemodialysis, failure to use the new graft by 12 weeks after access creation will be considered access site failure and the study will be terminated. For incident patients not yet on hemodialysis or prevalent patients whose new graft is not being used, patency of the access will be determined by monthly assessment of the graft for the presence of an audible bruit or a palpable thrill. Loss of both of these findings at any time in a patient whose access is not being used will be considered to be the primary event and the date of the endpoint will be the date of ascertainment by the study coordinator.

The primary endpoint will not include diagnostic studies (e.g., angiogram or ultrasound) that reveal a stenosis <50%.

#### 8. SECONDARY OUTCOME MEASURES

#### 8.1 Cumulative Patency: Time to Complete Access Site Failure

Complete loss of a functional access site is an outcome of major clinical importance. It is not economically feasible to continue the study drug and intensive monthly data collection for the duration needed for an adequately powered study of site failure. However, it is important to track this outcome at the closeout of the study to see if the trend is consistent with the effect seen for the study drug in the main trial. For this analysis, cumulative patency is the time from randomization to complete loss of the access site for dialysis regardless of the number of interventions required to restore or maintain patency. Loss of the access site is defined by the need to place a new access using new arteriotomy and venotomy incisions or by the abandonment of the prior access as defined by the need for a central venous dialysis catheter for a period of  $\geq 1$  month. Operationally the need for a new arteriotomy and venotomy sites will be detected by the need for a completely new site for the placement of the access. (Note that in most instances a chart review should not be needed to determine this endpoint). Procedures used to prolong the function of the access at the current site such as resection and replacement of part of the graft or changing just the site of the venous anastomosis will not be considered site failure). It is anticipated that a pharmacological agent that prolongs primary unassisted patency will also prolong cumulative patency even if the drug is stopped at the primary endpoint. The median cumulative patency in a control population without active flow monitoring and angioplasty is expected to be about 2 years [Hofstra, 1996 #60; Mattsson, 1997 #280; Kohler, 1999 #281]. An active access surveillance program will prolong access survival in the control population beyond 2 years but the exact duration is not well defined in the literature [Sands, 1995 #63; Safa, 1996 #101; Besarab, 1995 #62].

#### 8.2 Patient Survival

It is important that the study drug not produce any adverse consequences that might be worse than the measured outcome. Aspirin contained in Aggrenox is expected to cause an increase in minor and major bleeding events but is not expected to increase serious or fatal bleeding events. On the other hand, aspirin is known to decrease the rate of arterial thrombotic events in high risk populations. Given the high rate of cardiovascular death in the hemodialysis population, aspirin might actually improve overall patient survival. Due to the importance of this issue, time from randomization to death has been designated as a secondary outcome variable. However, it is recognized that the power of the study to detect a treatment effect on mortality is limited.

# 9. STATISTICAL DESIGN

#### 9.1 Sample Size Calculations

The rationale for each of the assumptions used to calculate the required sample size for the study is outlined below. All of the calculations are based on the primary outcome of primary unassisted patency. The power calculations assume a constant hazard rate for the primary outcome, with a one-year probability of access failure in the control group of 0.54. The calculations further assume an annual loss to follow-up of 22%, an annual dropout rate of 15%, and an annual dropin rate of 1%. Under the suggested predefined stopping rule (see below), a total of 1056 subjects will be required to have a 85% power to detect a 25% reduction in the rate of the primary outcome for Aggrenox compared to placebo. Under the assumption of a constant hazard rate, this corresponds to a 33% increase in median primary unassisted patency from 10.70 to 14.28 months. Assuming that there will be a total of 7 Clinical Centers with a total of 1136 new grafts placed per year, an enrollment rate of 31.0% would allow patient accrual to be completed by 3 years and the total study duration would not exceed 4 years. With the recommended stopping rule the expected study duration will be slightly under 3 years under both the null hypothesis of no treatment effect and the research hypothesis of a 25% benefit of Aggrenox.

Addendum: As of June 1, 2004 the study was extended to 48 months of recruitment with a minimum of 6 months of additional follow-up on the recommendation of the Data Safety and Monitoring Board (External Advisory Committee).

#### 9.1.1 Event Rate

Primary unassisted patency rates for upper extremity grafts vary with patient selection, surgical expertise as well as site and configuration of the graft (55, 56, 63, 64). Recent studies that mirror the circumstances of this study reveal one-year primary unassisted patency rates of between 23% - 49% (6, 55, 56, 81). Due to limits in ascertaining early access failures, data from the USRDS likely underestimates overall access failure rates (6). The remaining studies report one-year primary unassisted patency rates of between 23% - 43% (55, 56, 81). Since study patients will likely do somewhat better than average a one-year primary unassisted patency rate of 46% was determined for the primary power calculations (i.e., a one-year probability of access failure of 0.54).

#### 9.1.2 Effect Size

The study by Sreedhara found a 50% effect size for dipyridamole alone and 27% for dipyridamole plus aspirin to decrease thrombosis in new grafts (34). No other controlled trial of dipyridamole to prevent hemodialysis access failure has been reported. However, long-term follow-up of vein grafts used for coronary artery bypass have also found an effect size of 41% for aspirin plus dipyridamole to decrease the percent of veins that have a stenosis compared to placebo (45). Tempering these data is one retrospective report suggesting no effect of dipyridamole to prevent hemodialysis graft failure (33, 44). Looking at the effect of dipyridamole in the secondary prevention of occlusive arterial vascular disease (i.e., myocardial infarction and stroke), most studies have used a combination of aspirin and dipyridamole (82). The effect size in these studies was between 18% - 36% (82). However, in most studies the addition of dipyridamole was not shown to improve the outcome over aspirin alone (76). In contrast, in a large randomized, placebo-controlled double-blind study for secondary prevention of ischemic stroke involving 6602 patients, dipyridamole (200 mg bid; n=1654) was found to decrease the risk of stroke by 16% and the combination of aspirin plus dipyridamole (n=1650) reduced risk by 37% (47). In this study, low dose aspirin (25 mg bid) alone reduced the risk by 18% which is somewhat less than studies using a higher dose of aspirin (83). Nevertheless, this

large study demonstrates that dipyridamole alone is effective for secondary stroke prevention and the combination medication Aggrenox is better. Finally, with regard to restenosis after a vascular procedure, the data published to date would suggest no benefit of using lower doses of immediate release dipyridamole (57, 58, 74, 78). However, as discussed above these studies may not be relevant to angioplasty of venous lesions and the time-averaged concentration of dipyridamole would be much lower than that provided by Aggrenox. We are not aware of any clinical trials of Aggrenox after angioplasty in humans. However, dipyridamole has been effective in experimental models to prevent restenosis after angioplasty. Based on these studies and clinical estimates of what effect size would constitute a meaningful result, an effect size of 25% has been hypothesized for the primary outcome.

#### 9.1.3 Subject Loss or Modality Transfer

Based on the data from the HEMO Study we anticipate that the rate of patient death, transfer to another treatment modality or loss to follow-up will be 22%.

#### **Dropin and Dropout**

Based on prior experience in large scale clinical trials, the annual rate of dropouts (patients randomized to the Aggrenox arm who stop taking active drug) was assumed to be 15%. The annual rate of dropins (patients randomized to the placebo arm who receive Aggrenox or a related drug) was assumed to be 1%.

#### 9.1.5 Statistical Stopping Rule

The Steering Committee has recommended that the External Advisory Committee adopt an information-based stopping rule based on a boundary in which the study will be terminated early if therapy with Aggrenox is proven to be effective or the null hypothesis cannot be disproved under the current study design. Boundaries form the Wang-Tsiatis class (84) with shape parameters of 0 (corresponding to the O'Brien-Fleming stopping rule) are suggested for the boundary both for early rejection of the null hypothesis and early termination due to futility. A total of 6 looks equally spaced in information time are planned.

#### 9.2 Data Analysis

# 9.2.1 Interim Monitoring and Analysis

An independent External Advisory Committee will monitor the safety of the patients during the course of the study and to perform the interim efficacy analysis.

#### 9.2.2 Final Analysis

#### 9.2.2.1 Baseline analyses

To assess external generalizability, the demographic, clinical, and dialysis treatment characteristics of patients who are randomized will be summarized to characterize the study population and then contrasted with the characteristics of patients who are screened but not randomized. The randomized patients will also be compared to the general population of hemodialysis patients characterized in the USRDS. The specific eligibility and exclusionary criteria by which patients are excluded from randomization will be tabulated. Demographic and clinical characteristics will be compared among the Clinical Centers and between the treatment groups to identify any imbalances.

#### 9.2.2.2 Primary Analysis

The primary statistical analysis will compare the effects of the Aggrenox and placebo interventions on primary unassisted patency as in Section 7. This analysis will be conducted using a Cox proportional hazards regression analysis (85) with stratification by Clinical Center and graft location (lower arm vs. another site). ACE inhibitor or ARB usage at baseline and serum albumin at baseline will be included as pre-specified covariates. The comparison of the Aggrenox and placebo interventions in the primary analysis will be carried out using an intent-to-treat strategy in which patients are retained in their randomized groups regardless of their compliance to the treatments. A 2-sided hypothesis test will be conducted at the 5% level of significance.

In accordance with the intent-to-treat format, events defining the primary unassisted patency outcome which occur after medication stop points will be counted as events in the primary analysis. However, the primary Cox regression analysis will be censored at the following events: death, renal transplant, switch to peritoneal dialysis or home dialysis, or transfer to a center not participating in the trial. Censoring these events is consistent with previous studies of access survival (34, 56, 86-88), and is necessary because the alternative strategy of incorporating them in the primary outcome would unacceptably reduce the hypothesized treatment effect. However, because they occur frequently in dialysis patients, it is recognized that censoring these events exposes the primary treatment comparison to the possibility of bias due to informative censoring (89).

The cumulative incidence of events for the primary outcome will be summarized graphically by Kaplan-Meier survival curves in which death, transplant, modality switches, and transfers are censored. The Kaplan-Meier curves will estimate the distribution of unassisted patency assuming independent censoring in a hypothetical population where the censoring events are assumed not to occur. In addition to the standard Kaplan-Meier curves, we will summarize the marginal cumulative incidence of the composite outcome while treating death, transplant, and modality switches as competing risks (90, 91). In this approach, the cumulative incidence curves estimate the marginal cumulative probabilities of occurrence of the composite event while acknowledging the absence of the composite event following death, transplant or modality switches.

#### 9.2.2.3 Explanatory Analyses of the Primary Outcome

Explanatory analyses will be conducted to more fully characterize the relationship between the primary outcome, randomized group, and prognostic covariates based on interactive analysis of the data. Variable subset selection will be used to develop multivariable Cox regression models relating the hazard rate for access procedures to the randomized treatment groups and prognostic demographic factors, baseline biochemistry measurements, and other baseline variables. Nonparametric regression methods will be used to investigate possible nonlinear relationships between the hazard rate and prognostic factors (92, 93). Models with time-dependent covariates will be used to assess the association of the risk of access procedures with follow-up covariates (94), and interactions between Aggrenox and other factors will be investigated (95). The possibility of nonproportional hazards will be investigated by log-log plots (96) and by modeling the interaction of follow-up time with the Aggrenox - placebo comparison.

Sensitivity analyses to evaluate the possible influence of informative censoring in the primary Cox regression analysis will be conducted by taking advantage of the observations that several of the factors which have been found to be prognostic of the duration of graft patency are also related to the censoring variables. These include low serum albumin, greater age, diabetes, and a history of cardiovascular disease. Accordingly, the Cox-regression coefficients from the primary analysis will be compared to the coefficients from expanded Cox regression models which includes all baseline factors which are found to be associated with both the primary outcome and with at least one of the censoring variables. Second, recently proposed methods for survival curve estimation incorporating data from longitudinal prognostic covariates (97, 98, 99) will be used to estimate the time-to-occurrence of the primary composite outcome within the two treatment groups while accounting for follow-up blood

flow measurements prior to censoring. These methods would reduce the bias due to informative censoring due to any process in which the censoring is associated with the access blood flow measurements.

#### 9.2.2.4 Secondary Outcomes

Time from randomization to the secondary outcome of site failure will be analyzed using a Cox regression model similar to that used in the primary analysis, with the same stratification factors, adjustment for baseline serum albumin and the same censoring variables. Time from randomization to death, and time from randomization to the composite of death or site failure will also be analyzed by Cox regressions with the same stratification factors and adjustment for baseline albumin as in the primary analysis. As for the primary analysis, censoring events include renal transplant, switch to peritoneal dialysis or home dialysis, or transfer to a center not participating in the trial. Cox models with cause-specific hazard rates will be used to analyze the specific cause of the primary events (e.g., events may be classified as being triggered by stenosis or clotting).

The effect of Aggrenox on the change in access blood flow over time (considered as a continuous variable) will be examined by longitudinal mixed effects models (100) or generalized estimating equations (101, 102). Joint models incorporating the longitudinal changes in access blood flow and the time-to-first access procedure will also be considered (103).

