Use of angiotensin converting enzyme inhibitors has recently been reported in two retrospective studies to have a strong effect to prevent access failure (119, 120). The results are preliminary, however, the use of ACE inhibitors in dialysis patients is increasing. If ACE inhibitors or ARBs do have a large effect on access survival then this could impact on the response to Aggrenox. Therefore, whether a patient was on an ACE inhibitor or ARB at baseline will be included as a prespecified covariate in the primary analysis. The use of these agents will not be controlled and may change during the course of the study. The ongoing use of these agents will be recorded at the monthly visits and that data will be used to further analyze for a possible relationship between use of these agents and access failure. In addition, hypoalbuminemia has been reported to be a strong risk predictor of access failure (55, 63, 64). Therefore, serum albumin at baseline will be included as a second prespecified covariate in the primary analysis. Other potential prognostic factors such as diabetes and vascular disease have not been consistently shown to be strong predictors of access failure, and will not used as stratification factors or as covariates in the primary analysis.

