# 6. DATA COLLECTION

#### 6.1 Baseline Data

The baseline evaluation is designed to: 1) ensure that subjects meet the inclusion/exclusion criteria, 2) obtain information regarding demographics, access history, medications, and medical history that may affect treatment response and risk of access failure, and 3) obtain information on medical history and laboratory tests to ensure that patients are not at risk for developing

complications of therapy. Data should be collected as close to the time of graft creation as possible but no longer than 45 days prior, and should include:

- 1. Patient identification demographic information (age, gender, race)
- 2. Patient's mailing address for study medication. If no suitable home address, medication will be mailed to the dialysis unit to provide to the patient
- 3. Date of enrollment
- 4. Date of ESRD; start date for hemodialysis
- 5. Cause of ESRD (diabetes, hypertension, polycystic kidney disease, glomerulonephritis, interstitial nephritis, hereditary nephritis, other)
- 6. Access history
  - a. Prior arteriovenous access attempts number, type, location, date(s) placed
  - b. Prior central catheter placements (subclavian or int. jugular) yes/no; right, left or both
    c. Current central catheter type, site, date placed
- 7. Diagnoses (history of diabetes (duration, nephropathy, retinopathy, neuropathy), hypertension (duration), vascular disease (myocardial infarction, CABG, CHF, angina, stroke, TIAs, peripheral vascular disease, amputations), coagulopathy, or hyperlipidemia
- 8. List of current medications
- 9. Tobacco use (how much, age at start, currently smoking (yes/no), if not, when habit stopped
- 10. Quality of life questionnaire
- 11. Blood pressure & pulse predialysis, sitting position
- 12. Height and weight
- 13. Periodontal disease (no obvious cavities or gingivitis, cavities or gingivitis, or edentulous)
- 14. Examine arms to note scars and evaluate number and location of any current functional accesses and previously failed access sites
- 15. Look for presence of current central catheter Note type and location.
- 16. Baseline biochemical measurements most recent within the last 45 days, record date CBC (hemoglobin, platelet count), and albumin.

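### Optional improvement, not an error: the time-to-death model adjusts for albumin only, and adding age, diabetes and cardiovascular history could raise power by 0 to about 6 points at no data cost

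*Protocol*

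**What the plan says.** Protocol Section 9.2.2.4 specifies Cox models for time to death and for death or site failure "with the same stratification factors and adjustment for baseline albumin as in the primary analysis". The strata are Clinical Center and graft location (Section 9.2.2.2). Baseline albumin is the only covariate named for these models; the primary model's ACE inhibitor/ARB term is not carried over.

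The only reasons given for choosing covariates are in Section 3.3, and they concern the graft. Albumin enters because "hypoalbuminemia has been reported to be a strong risk predictor of access failure". Diabetes and vascular disease are left out because they "have not been consistently shown to be strong predictors of access failure".

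Section 9.2.2.3 says that several factors "prognostic of the duration of graft patency are also related to the censoring variables", and continues: "These include low serum albumin, greater age, diabetes, and a history of cardiovascular disease". The censoring events of the primary analysis are listed in Section 9.2.2.2 as "death, renal transplant, switch to peritoneal dialysis or home dialysis, or transfer to a center not participating in the trial".

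On mortality as an outcome, Section 8.2 says "it is recognized that the power of the study to detect a treatment effect on mortality is limited" and gives no figure. Section 6.1 collects age (item 1), and diabetes and the vascular diagnoses (item 7), at baseline.

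**The concern.** A covariate set justified by graft failure is reused for an outcome with different determinants. Of the four factors that the protocol relates to its censoring events, the death model keeps one and leaves out three that are already in the database.

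In a Cox model, leaving out true predictors of the outcome costs power even in a randomized comparison. Section 8.2 designates death as a secondary outcome for two reasons: the drug should not do harm that outweighs its effect on the graft, and it might improve survival. An inexpensive gain in precision is useful for either purpose. The question concerns the mortality model only, not the covariates chosen for primary patency.

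**Working it through.** **The protocol's own figures.** No power or event count is stated for death, so only the primary-outcome inputs can be reproduced. Control median: 12 × ln 2 / (−ln 0.46) = 10.71 months. Dividing by 0.75 gives 14.28 months. Accrual: 1136 × 0.31 × 3 = 1056. A log-rank calculation with the stated loss, dropout and dropin rates, and an inflation of 1.118 for the six-look stopping rule, gives 86.9% power against 85% stated. The design inputs can be relied on.

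**Inputs for death.** N = 1056, 1:1 allocation. Control mortality 16% per year (Section 1.3). Total loss including death 22% per year (Section 9.1.3). Uniform accrual over 3 years, 4 years in total (Section 9.1). Two-sided 5% level (stated for the primary test, assumed here).

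**Expected deaths at hazard ratio 0.75.**
- Control death hazard: −ln 0.84 = 0.1744. Total hazard: −ln 0.78 = 0.2485. Other loss: 0.0741.
- Aggrenox death hazard: 0.75 × 0.1744 = 0.1308. Total with other loss: 0.2049.
- With death hazard λ, total hazard s and follow-up uniform on 1 to 4 years, P(death) = (λ/s) × [1 − (e^(−s) − e^(−4s))/(3s)].
- Control: 0.702 × (1 − 0.550) = 0.316. Aggrenox: 0.638 × (1 − 0.609) = 0.250.
- Deaths: 528 × 0.316 + 528 × 0.250 ≈ 299.

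**Power without covariate effects (Schoenfeld).** Φ(√299/2 × ln(1/0.75) − 1.96) = Φ(2.487 − 1.960) = Φ(0.527) = 70%. The same steps give:

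| True hazard ratio | Deaths | Power |
|---|---|---|
| 0.85 | 313 | 30% |
| 0.80 | 306 | 50% |
| 0.75 | 299 | 70% |
| 0.63 (the 37% reduction cited in Section 1.5) | 280 | 97% |

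Under the extended calendar in the Section 9.1 addendum (48 + 6 months, N still 1056), the figures at 0.75 are 293 deaths and 69%.

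**Gain from the three covariates.** Simulated trials, N = 1056, 3 + 1 years, 6000 replicates per setting, true hazard ratio 0.75. Both models were fitted in each setting. The documents give no prognostic strengths, so all are assumed. Gains are taken from unrounded powers.

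| Assumed hazard ratios for death (age per SD / diabetes / cardiovascular history) | Albumin only | Plus the three | Gain in points |
|---|---|---|---|
| 1 / 1 / 1 (no association) | 70.0% | 70.0% | 0 |
| 1.2 / 1.2 / 1.2 (weak) | 68.8% | 69.3% | +0.6 |
| 1.4 / 1.3 / 1.5 (moderate) | 65.8% | 68.5% | +2.7 |
| 1.65 / 1.6 / 1.8 (strong) | 61.6% | 67.9% | +6.4 |

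At a true hazard ratio of 0.85 the gain is +0.2 to +3.3 points. With no treatment effect and moderate strengths (the one null setting run), type I error is 4.8% for both models.

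A second simulation used follow-up uniform on 0.5 to 4.5 years, about 300 deaths and 4000 replicates. At a hazard ratio of 0.75, power rises from 67.3% to 70.0% with moderate predictors (+2.7) and from 65.6% to 71.0% with strong ones (+5.4). Neither simulation included the center and graft-site strata.

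**The case against.** The strongest reply is that nothing here is wrong. The model is valid and pre-specified, its type I error is unaffected, and adjustment beyond the main model is often left to a statistical analysis plan, which is not available. This stands as far as calling it an error goes. It does not remove the suggestion, because the protocol itself fixes the covariate set for death and gives no mortality-based reason for it.

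Several stronger readings are tempting, and the documents do not support them:

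- *That albumin is off-target for death.* It heads the same Section 9.2.2.3 list as the other three, so by the protocol's own text it has the same link to the censoring events.
- *That the protocol names age, diabetes and cardiovascular history as predictors of death.* The stated link is to the censoring variables as a group, which also include transplant, modality switch and transfer. Section 1.3 says only that fewer diabetic patients may be one reason why the earlier unpublished trial's population differed. Section 8.2 notes the high rate of cardiovascular death. These make the link to death plausible but do not quantify it.
- *That mortality is underpowered.* Section 8.2 says limited and gives no number. At the only dialysis mortality effect cited, a 37% reduction, power is already about 97%, with almost nothing to gain.
- *That the albumin-only hazard ratio is biased.* The second simulation gave, for example, 0.759 with albumin only against 0.745 with all four covariates. This largely reflects the non-collapsibility of the hazard ratio: the two models target different conditional effects.
- *That the death-or-site-failure composite would gain equally.* No calculation covers it. Section 3.3's view that diabetes and vascular disease are inconsistent predictors of access failure weakens the case there.

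Mortality is also not the only harm check. Deaths after a recorded bleed are centrally reviewed (Section 6.2.6), and the External Advisory Committee compares adverse events between arms (Section 10).

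**Conclusion.** The point holds as a low-cost efficiency gain on a secondary outcome, not as an error or contradiction. At a true hazard ratio of 0.75 and about 299 deaths, the gain is 0 points if the three factors are unrelated to death, about 0.6 if they are weak predictors, 2.7 if moderate, and 5 to 6 if strong. No setting showed a material loss.

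The size rests on assumed prognostic strengths, on 16% annual mortality with 22% total annual loss, and on simulations without the strata. The documents cannot narrow the range further.

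**What to change.** In Section 9.2.2.4, pre-specify these covariates for the time-to-death Cox model, with stratification unchanged: baseline albumin, age, diabetes (yes/no), and history of cardiovascular disease (yes/no, meaning any of the vascular diagnoses listed in Section 6.1 item 7). The same set may be used for death or site failure, but no gain has been shown there.

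The cost is a sentence or two of analysis wording and no new data. Treatment plus four covariates is five parameters, or about 299/5 ≈ 60 deaths per parameter. There are two downsides. The reported hazard ratio becomes conditional on more covariates. The cardiovascular-history variable, which Section 6.1 collects as separate diagnoses, must be defined before unblinding.
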